- By pain we mean that the place where you were injected hurts even when it isn't touched.

If you experience pain or itching at the injection site, use the following categories to describe how severe these symptoms were. If you don't experience one or more of these symptoms, mark the **NONE** box.

- **Mild** 😊 I only had a little discomfort. I could still use my arm like always.
- **Moderate** 😕 I noticed the discomfort and didn't use my arm as much as usual.
- **Severe** 😟 I really noticed the discomfort. It kept me from doing something I wanted or had to do.

Redness, swelling, and bruising

Some people experience redness, swelling, or bruising in the area where they were injected. If you experience redness, swelling, or bruising, measure the area using the measuring tool you were provided, and record the measurement in the space provided.

To measure the area of redness, swelling, or bruising, do the following:

- Place the measuring tool over the area where you were injected, with the dot over the center of the area.
- Select the circle where the longest part of the area touches the line.
- If the area is in between two circles, select the larger circle.

For example, the area shown to the right measures 3 centimeters (cm) because it is touching the 3cm line.

General and Other Symptoms or Medications

If you have additional symptoms that are not listed, or if you sought medical care for any reason from a health care provider (e.g. doctor's office, emergency room), or if you took any medications, these should be listed in the spaces provided. Please designate any symptoms as Mild, Moderate, or Severe.

- **Mild** 😊 I only had minor discomfort. I went about my usual activities.
- **Moderate** 😕 I noticed the symptom. It bothered me enough that I didn't do as much as I usually do.
- **Severe** 😟 I really noticed the symptom. It kept me from doing something I wanted or had to do.

Day 6: 6 Days After Injection Subject #: _____ Date: _____ / _____ / _____

The items on this page refer to the time between midnight of last night and 11:59 p.m. today (Day 6). If any of the symptoms you reported on previous pages have not gone away ("resolved"), you will need to let the Site Coordinator or Doctor know.

Temperature

Evening Temp.: _____ °C or °F (circle one)	Time Taken: _____ AM or PM (circle one)
--	---

General Symptoms

If you experience any of these symptoms, mark the box that describes your worst symptom until 11:59 p.m. tonight (Day 6). See General Instructions on page 14 for more information.

Symptom	None	Mild	Moderate	Severe
Unusually tired/feeling unwell				
Muscle aches				
Headache				
Nausea				
Joint pain				

Injection Site Symptoms

If you experience an injection site symptom, mark the box that describes your worst symptom until 11:59 p.m. tonight (Day 6). See General Instructions on page 14 for more information.

Symptom	None	Mild	Moderate	Severe
Pain				
Itching				

Redness, Swelling, or Bruising	None	Provide Maximum Measurement
Redness		cm at the longest part
Swelling		cm at the longest part
Bruising		cm at the longest part

Other Symptoms

If you experience symptoms other than the ones above, write them in the space below according to the General Instructions on page 14.

Did you experience any other symptoms? Yes No

Symptom or Medical Event	Mild	Moderate	Severe
			
			
			
			

Did you take any medications? Yes No

If yes, please list out the name(s) and dosage(s) below:

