3.2 Primary Safety Endpoints

Safety will be described for all subjects:

1. Occurrence, nature (MedDRA systemic organ class [SOC] and preferred term [PT]), time to onset, number of days of occurrence, intensity, and relationship to investigational product of injection site reactions and systemic reactions occurring up to 7 days after administration of the investigational product
2. Occurrence, nature (MedDRA SOC and PT), time to onset, relationship to investigational product and outcome of SAEs throughout the study

3. Visual analogue scale (VAS) and (see comment) scores for injection site pain up to 7 days after administration of the investigational product
4. Occurrence of out-of-range from baseline biological test results up to 7 days post-last dose

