9.4.6 Visual Analog Scale

At select times after EP, participants will complete VAS questionnaires. A VAS consists of a horizontal line, 10 cm in length, anchored by word descriptors at each end (no pain = 0 cm; worst pain = 10 cm). Immediately after injection/EP, the participant will be instructed to mark on the line, the point that they feel represents the pain experienced related to the injection/EP procedure. The VAS will be administered immediately after EP and 5 and 10 minutes later after each injection, which are separated by 30 minutes. The VAS score is determined by measuring in centimeters from the left-hand end of the line to the point that the patient marks.

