9.8.2 Staff Evaluations

Study staff should evaluate each unique memory aid entry according to “Toxicity Grading Scale for Healthy Adult and Adolescent Volunteers Enrolled in Preventive Vaccine Clinical Trials”, issued in September 2007 ([Appendix B: Toxicity Grading Scale](#)). Any memory aid entry determined to meet the criteria for a Grade 1 or higher adverse event must be documented as an adverse event. If the reminder memory aid entry does not meet the criteria of a Grade 1 or higher AE as per the toxicity grading scale, clinical judgment can be used to determine whether the entry should be recorded as an AE. For cases

where the reminder memory aid entry and final AE reporting (i.e., grading) do not agree, the reasoning must be recorded in the source documents.

The Investigational product administration procedure consists of insertion of the CELLECTRA™ 2000 5P-IM electroporation array needles (electrodes) through the skin and into the underlying muscle, and intramuscular injection of the Investigational product followed by delivery of the electroporation pulses. This procedure is broadly described as administration because it involves more than the injection of a drug. Attributing any reaction (e.g., pain, erythema, swelling) that is observed at or near the site of the Investigational product administration procedure to injection of the Investigational product or administration of the electroporation pulses will be difficult and is not necessary. Consequently, reactions arising from the Investigational product administration procedure may be reported as administration site or injection site reactions.

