10.9 Safety and Toxicity Management

The Medical Director will be responsible for the overall safety monitoring of the study. Safety assessments include the following:

- Adverse events utilizing the "Toxicity Grading Scale for Healthy Adult and Adolescent Volunteers Enrolled in Preventive Vaccine Clinical Trials", issued September 2007 ([Appendix B: Toxicity Grading Scale](#)).
- Local pain immediately after Investigational product administration and at select times using a VAS.
- Clinically significant laboratory abnormalities (e.g., CBC, chemistry, hematology, coagulation, CPK, urinalysis, ECG) compared to baseline.
- Clinically significant changes to vital signs compared to baseline.

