11.4 Sample Size/Power

Our analyses will focus on estimation, and not on hypothesis testing. No formal power analysis is applicable to this study. We will, however, describe the precision available for descriptive statistics used to summarize the data. For proportions, our samples will be either N=3, N=5, N=6, or N=24, with target estimates of 30% DLTs. CI width varies with event frequency, as shown in Table 6. Our 90% CIs will be no wider than 0.694 for the samples of 6, or 0.361 for the overall sample of 24. For continuous measures, samples of 6 and 24 will yield standardized CIs of 1.64 SDs and 0.70 SDs respectively.

Table 6. Width of 95% CIs

Sample	Pr=0.05	Pr=0.1	Pr=0.2	Pr=0.3	Pr=0.4	Pr=0.5
N=3	0.676	0.716	0.785	0.835	0.865	0.875
N=5	0.510	0.562	0.647	0.703	0.734	0.744
N=6	0.456	0.512	0.598	0.653	0.684	0.694
N=24	0.191	0.239	0.300	0.335	0.355	0.361

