15 APPENDICES

15.1 Appendix A: Participant Memory Aid

To be completed by Staff:

Participant ID: Site Number – Participant Number	Post-Vaccination  Day 0  Day 3
Today's date: dd/mm/yyyy	Timepoint:  Immediately after  5 minutes after  10 minutes after  Other: _____
Actual time: 24-hour clock	
VAS Pain Score: cm	
Administrator Comments: _____ _____ _____	

To be completed by Participant:

PAIN ASSESSMENT

Mark the line below using a single stroke at the point that you feel best represents the pain experienced related to the electrical pulses.

NO PAIN _____ WORST PAIN

Participant Reminder Diary

SARS-CoV-2-dMAB01

Subject #: _____

Injection Date: _____

Study Arm: _____

Note to Participant:

For questions or problems, please contact your Site Coordinator.

Name: _____

Telephone: () _____

Email (optional): _____

General Instructions

Temperature

Take your temperature orally around the same time each evening, using the thermometer provided and record it in the space provided. Also record the time at which you took your temperature. If you recently drank very hot or cold liquids, wait 15 minutes before taking your temperature.

Injection Site Symptoms

Pain and itching

Some people experience pain in the area where they were injected. Some people may also experience itching in the area where they were injected.

- By pain we mean that the place where you were injected hurts even when it isn't touched.

If you experience pain or itching at the injection site, use the following categories to describe how severe these symptoms were. If you don't experience one or more of these symptoms, mark the **NONE** box.

- **Mild** 😊 I only had a little discomfort. I could still use my arm like always.
- **Moderate** 😐 I noticed the discomfort and didn't use my arm as much as usual.
- **Severe** 😟 I really noticed the discomfort. It kept me from doing something I wanted or had to do.

Redness, swelling, and bruising

Some people experience redness, swelling, or bruising in the area where they were injected. If you experience redness, swelling, or bruising, measure the area using the measuring tool you were provided, and record the measurement in the space provided.

To measure the area of redness, swelling, or bruising, do the following:

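### The printed VAS form asks only about pain from the electrical pulses, which is narrower than Section 9.4.6 and than primary safety endpoint 3

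*Protocol*

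**What the plan says.** The Protocol describes the target of the same 10 cm scale in several places.

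- **Section 3.2, endpoint 3 (repeated in the Synopsis, Section 1.1):** VAS "scores for injection site pain up to 7 days after administration of the investigational product".
- **Section 9.4.6:** the participant is told to mark "the point that they feel represents the pain experienced related to the injection/EP procedure". On timing, "The VAS will be administered immediately after EP and 5 and 10 minutes later after each injection".
- **Section 10.9:** the scale is listed among the safety assessments as "Local pain immediately after Investigational product administration and at select times using a VAS".
- **Section 15.1, Appendix A, the VAS form:** the participant marks the point that "best represents the pain experienced related to the electrical pulses".

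Section 9.8.2 also bears on this. It treats needle insertion, injection and pulses as one administration procedure. Assigning a site reaction, with pain as an example, to the injected product "or administration of the electroporation pulses will be difficult and is not necessary". It adds that "reactions arising from the Investigational product administration procedure may be reported as administration site or injection site reactions".

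**The concern.** The form is the instrument of a primary safety endpoint, and its question is narrower than both the endpoint and the procedure section. It asks the participant to separate pulse pain from the rest, which Section 9.8.2 says is hard and need not be done.

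What is at stake is the part of the pain that the printed question leaves out: needle insertion, injected volume and formulation. Section 4.1 says that the added cohorts are meant to examine both alternative EP parameters and modified formulations. A question confined to the pulses suits the first aim and, taken literally, misses the second. An analysis plan cannot repair this afterwards, because it cannot recover an answer to a question that was not put.

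**Working it through.** The point concerns wording, so there is no plan figure to reproduce. The check has three steps.

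**1. What each text includes**

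| Source | Target of the score | Needle, volume and formulation pain | Pulse pain |
|---|---|---|---|
| Section 3.2 and Synopsis | Injection site pain | Included | Included, since Section 9.8.2 lets procedure reactions be reported as injection site reactions |
| Section 9.4.6 | Injection/EP procedure pain | Included | Included |
| Section 10.9 | Local pain after administration | Included | Included |
| Appendix A form | Electrical pulse pain | Not included, read literally | Included |

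The first three can be read as one construct. The form is the outlier, and no section explains the difference.

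**2. How many readings carry the prompt**

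Readings per participant = 2 injections per dosing day × 3 time points × number of dosing days (Sections 4.1 and 9.4.6, Table 2).

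- A1, A2: 2 × 3 × 1 = 6
- B to F: 2 × 3 × 2 = 12
- G: 2 × 3 × 4 = 24

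The form has one prompt, with tick boxes for the time points, so all of these readings carry it.

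**3. What differs between cohorts (Table 2, per injection)**

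| Cohort | Volume (mL) | Hylenex (U) | Each dMAb (mg) | OpBlock |
|---|---|---|---|---|
| A1 | 0.5 | 68 | 0.5 | 0078 |
| A2 | 1 | 135 | 1 | 0078 |
| B | 0.5 | 66.5 | 0.5 | 0078 |
| C | 1 | 135 | 1 | 0078 |
| D | 0.25 | 34 | 0.25 | 0078 |
| E | 0.70 | 75 | 2 | 0078 |
| F | 0.55 | 75 | 0.5 | 0070 |
| G | 0.55 | 75 | 0.5 | 0078 |

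Eight cohorts give 8 × 7 / 2 = 28 pairs. Cohort F is in 7 of them, so 28 − 7 = 21 pairs share the same OpBlock. Of those 21, only A2 and C match on volume, Hylenex and DNA dose, which leaves 20 that differ in at least one. Some differ very little: A1 and B by 68 − 66.5 = 1.5 U only. For most contrasts, then, what varies is the injectate, and the printed question does not ask about it.

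The volumes are those of Table 2. Section 4.2 gives about 2 mL for cohort E. Those two passages need reconciling in their own right, and nothing here depends on which one stands.

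**The case against.** The case for leaving this alone has real content.

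- **Pulse pain belongs to administration site pain.** The pulses follow the injection immediately and Section 9.8.2 does not separate the two. A reader might infer that the form cannot give injection site pain at all. The documents do not support that: the form captures one component of it.
- **The spoken instruction may be broader.** Section 9.4.6 says that the participant will be instructed to rate the procedure. If staff say this aloud, the marks may reflect the wider construct despite the print. A reader might conclude that every score so far is pulse pain and should be relabelled. That goes too far, because the documents do not show which instruction prevailed.
- **Timing does not sort the readings.** A reader might infer that the 5 and 10 minute readings are the faulty two of every three, because no pulse is being delivered then. But the first reading also comes after EP, so none is taken during a pulse and the split separates nothing. A missing current-pain anchor is no contradiction either, since Section 9.4.6 has none.
- **Injection site pain is recorded elsewhere.** The diary asks for it daily by severity category with no mention of pulses (Appendix A). Staff assess local pain 30 minutes after each injection and at later visits (Sections 7.3 to 7.6 and 9.4.1).
- **No decision rests on the VAS.** The DLT criteria (Section 10.10) and stopping rules (Section 10.11) do not use it. Analysis is estimation only; Section 11.4 says "No formal power analysis is applicable to this study".

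These points limit the consequence but do not remove the mismatch. The diary starts that evening and staff assess at 30 minutes, neither by VAS, so neither supplies the 0 to 10 minute scores. The possible spoken instruction means that participant and staff may be working from two different questions.

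**Conclusion.** The point holds as a contradiction within the Protocol. The Appendix A prompt is narrower than Section 9.4.6 and than endpoint 3, and every VAS reading is taken under it: 6, 12 or 24 per participant by cohort. Read literally, needle, volume and formulation pain fall outside the 0 to 10 minute scores, in a design where 20 of the 21 cohort pairs with the same OpBlock differ in the injectate.

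The size of any effect on the scores is unknown. The Protocol gives no VAS data, does not say how far pain depends on volume, Hylenex or DNA dose, and does not say how participants understand the prompt. A reader might infer that cohort comparisons of VAS pain are biased; the documents show only that they could miss injectate pain. The conclusion assumes that participants see the form as printed and that it carries weight beside any spoken instruction. It is worth correcting because it touches the instrument of a primary safety endpoint, but no escalation or stopping decision depends on it.

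**What to change.** - On the Appendix A form, replace the reference to the electrical pulses with the Section 9.4.6 construct, the injection/EP procedure, and keep the wording identical at all three time points. Section 9.4.6 then needs no change. A new prompt about pain felt at that moment would bring in a further construct.
- Describe endpoint 3 in Sections 1.1 and 3.2 in the same terms, so that endpoint, procedure and form name one quantity.
- Footnote VAS scores already collected as obtained under the printed pulse prompt. Do not relabel them all as pulse pain.

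The cost is one line on the form, a matching edit to the endpoint in two places, and a table footnote. If some cohorts were scored before the change and others after, comparisons between them need that footnote as a caveat. No dose, schedule or clinical rule is affected.

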The CELLECTRA™ EP device can efficiently transfer plasmid DNA into cells to enable gene expression. This method of delivery has great potential for gene transfer and prophylactic and therapeutic vaccination, as has been demonstrated in animal studies¹⁶. EP has been extensively used in large animal species, such as dogs, pigs, cattle, and NHP, to deliver therapeutic genes that encode for a variety of hormones, cytokines, enzymes or antigens¹⁷ that can activate both cellular and humoral responses in animal models^{16,18}. The IM delivery of DNA with EP is well studied, and optimum conditions for plasmid uptake and expression are described for therapeutics, vaccines and tumor animal model systems^{19,20}. Inovio Pharmaceuticals has developed the CELLECTRA™ 2000 device which utilizes a novel constant current process for IM EP¹⁷.

2.3 **Risk/Benefit Assessment**

In accordance with the International Conference on Harmonization (ICH), this study has been designed to minimize risk to study participants. Potential risks of study products and administration from studies using similar plasmids with the identical DNA backbone are listed in [Table 1](#).

The potential side effects of treatment with the investigational products may include but are not limited to discomfort related to the inoculation administration and electroporation technique such as local edema, swelling, or pain. Systemic side effects observed with vaccines based on the identical backbone have been demonstrated to be generally minimal in more than 3500 participants. The potential benefit is to determine whether this inoculation could generate immune responses with potential to be sufficient as prophylactic treatment for those at risk for SARS-CoV-2 virus infection.

Table 1. Expected Risks of dMAb AZD5396 and dMAb AZD8076 and Hylenex® Recombinant (Hyaluronidase) Delivered IM with EP using CELLECTRA™ 2000 with side port needle

Frequency ^a	Event
Very Common (≥10%)	Mild Injection site pain or tenderness Moderate Injection site pain or tenderness Injection site erythema or redness Injection site swelling, hardness, or scabbing Injection site pruritus Not feeling well (fatigue, muscle aches, joint pain or headache)
Common (≥1% to <10%)	Pyrexia
Uncommon (≥0.1% to <1%)	Severe Injection site pain or tenderness Injection site bruising Nausea, lightheadedness or dizziness
Rare (≥0.01% to <0.1%)	None
Very Rare (<0.01%)	Allergic reaction

^a Defined per CIOMS

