4 STUDY PLAN

4.1 Study Design

This will be a Phase 1, open label, single center, dose escalation study to evaluate the safety, tolerability, and pharmacokinetic profile of mAb AZD5396 and mAb AZD8076 following delivery of optimized dMAb AZD5396 and dMAb AZD8076 with different doses of Hylenex® Recombinant, administered by intramuscular injection (IM) followed immediately by electroporation (EP) using the CELLECTRA™ 2000 with side port needle device, in a five-dose (8 cohort) regimen in healthy adults.

Up to 50 healthy volunteers 18 to 60 years of age will be enrolled in this study and evaluated across eight cohorts (n=3 to 6 per cohorts A1, A2, B, C, and D; n=5 per cohorts E, F, and G). Participants will be administered dMAb AZD5396 and dMAb AZD8076 at a five-dose level of each plasmid:

- 0.5 mg single-dose (cohort A1),
- 1 mg single-dose (cohort A2),
- 1 mg two-dose (cohorts B and F),
- 2 mg two-dose (cohort C),
- 0.25 mg two-dose (cohort D),
- 4 mg two-dose (cohort E), and
- 2 mg four-dose (cohort G).

Participants will receive two injections (one per dMAb) into the arm (deltoid)/leg (quadriceps) region at Day 0 alone (groups A1 and A2) or on day 0 and 3 (groups B-F) or on days 0, 3, 28, 31 (cohort G). Injections may be given in different arms or in an arm (deltoid) and a leg (quadriceps). If preferred or needed both doses can be done in the deltoid region or the lateral quadriceps, although the injections should be in different areas separated by at least 2 cm. The Day 3 injections may repeat an area already used on Day 0 as long as separated by at least 2 cm. The Day 31 injections may repeat an area already used on Day 28 as long as separated by at least 2 cm. The Day 28 injections may repeat an area already used on Day 0 or Day 3 injections with no separation required given the time span between injections.

This study will adhere to a dose escalation scheme as described in [Figure 2](#).

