9.4.1 Physical Exam and Targeted Physical Assessments

A full physical examination will be conducted during screening and at study discharge. A targeted physical assessment (physical exam focused on the area of specific symptoms) will be performed at other visits as determined by the Investigator or directed per participant complaints.

Injection Site Reaction

Injection site reaction assessed 30 minutes post injection and at all subsequent visits up to Day 10. Systemic and local reaction assessment consists of evaluation of the following:

Systemic: hypotension, hyperhidrosis, erythema, headache, dizziness, myalgia, arthralgia, fever, peripheral edema; and

Local reactions: pain, pruritus, erythema, swelling, scab, infection.

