When evaluating administration (injection) site reactions throughout the study, it is most important to be as specific as possible by selecting the most appropriate term (see [Table 5](#) below) and use the grading scale as listed in the Toxicity Grading Scale for Healthy Adult and Adolescent Volunteers Enrolled in Preventive Vaccine Clinical Trials, issued September 2007. Administration (injection) site reactions and administration site pain will be evaluated starting immediately and at 5 and 10 minutes following injection/EP. In addition, other events associated with administration (injection) site reactions (e.g., hematoma, infection or necrosis) should also be reported with preferred terms specific for administration (injection) site reactions. Injection site systemic and local reaction assessment that consists of evaluation of the following: General: hypotension, hyperhidrosis, erythema, headache, dizziness, myalgia, arthralgia, fever, peripheral edema, and local reaction: pain, pruritis, erythema, swelling, scab, infection. Non-injection site AEs will be assessed during the entire time while at the investigator site.

Table 5. Grading Scale for Injection Site Reactions

Local Reaction to Injectable Product (Grade)	Mild (1)	Moderate (2)	Severe (3)	Potentially Life Threatening (4)
Pain	Does not interfere with activity	Repeated use of non-narcotic pain reliever >24 hours or interferes with activity	Any use of narcotic pain reliever or prevents daily activity	Emergency room visit or hospitalization
Tenderness	Mild discomfort to touch	Discomfort with movement	Significant discomfort at rest	ER visit or hospitalization
Erythema/Redness ^a	2.5-5 cm	5.1-10 cm	>10 cm	Necrosis or exfoliative dermatitis
Induration/Swelling ^b	2.5-5 cm and no interference w/ activity	5.1-10 cm or interferes with activity	>10 cm or prevents daily activity	Necrosis

September 2007 “FDA Guidance for Industry—Toxicity Grading Scale for Healthy Adult and Adolescent Volunteers Enrolled in Preventive Vaccine Clinical Trials”

- In addition to grading the measured local reaction at the greatest single diameter, the measurement should be recorded as a continuous variable
- Should be evaluated and graded using the functional scale as well as the actual measurement.

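### The participant diary does not match the protocol's injection sites or grading scale: pain and itching are anchored to arm use, and tenderness on touch has no entry

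*Protocol*

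**What the plan says.** The first primary safety endpoint (3.2) covers occurrence, onset, number of days, intensity and relationship of "injection site reactions and systemic reactions occurring up to 7 days after administration of the investigational product". Under 9.8.1 participants record reactions at home in the memory aid, which is a source document. Under 9.8.2 staff evaluate each entry on the September 2007 toxicity scale, and anything of Grade 1 or above becomes an adverse event.

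**Injection sites.** Section 4.1 states: "Participants will receive two injections (one per dMAb) into the arm (deltoid)/leg (quadriceps) region". Section 9.5 describes a deltoid and a lateral quadriceps injection on the same side, with both in one region if preferred or needed. The two sections differ in detail, but both provide for leg injections.

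**Diary anchors.** For pain and itching, Mild refers to using the arm as always, and Moderate reads "I noticed the discomfort and didn't use my arm as much as usual". Severe is worded by general activity. Redness, swelling and bruising are measured in centimetres.

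**Diary definition of pain.** "By pain we mean that the place where you were injected hurts even when it isn't touched". Participants without a symptom mark NONE. There is no tenderness row.

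**Protocol on tenderness.** Table 5 grades it separately from pain, with Grade 1 being "Mild discomfort to touch". Table 1 (Section 2.3) includes "Mild Injection site pain or tenderness" among very common risks (10% or more). The staff list in 9.4.1 reads "Local reactions: pain, pruritus, erythema, swelling, scab, infection", and the list in 9.8.2 names the same six items.

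**The concern.** The diary is the day-by-day source for reaction intensity between clinic visits. In cohorts A1 and A2, Table 3 has no visit between Day 0 and Day 7. Two features of the form do not fit the rest of the protocol.

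First, a participant with a sore thigh is asked to rate it by use of the arm. Nothing in the Mild and Moderate wording tells that participant how to report limited walking.

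Second, a participant whose site hurts only when touched correctly marks NONE for pain and then finds no row for what was felt. The staff checklist does not prompt for it either. Intensity and occurrence of local reactions are part of a primary endpoint in cohorts of 3 to 6, so a few missed or shifted entries are visible in the results.

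**Working it through.** No figure in the protocol is under test, so the check sets the passages side by side.

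| Item | Diary (Appendix A) | Table 5 | Match |
|---|---|---|---|
| Pain, lower two levels | Arm use | Interference with activity, or repeated non-narcotic analgesic | Not for a leg site |
| Pain, Severe / Grade 3 | Prevented something wanted or required | Prevents daily activity, or any narcotic analgesic | Diary threshold is looser |
| Tenderness | No row; outside the pain definition | Four separate grades | None |
| Redness, swelling | Centimetres | Centimetres (swelling also functional) | Largely |

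Table 5 grades four local reactions (pain, tenderness, erythema, induration/swelling). The diary has a listed row for three; tenderness is the one without.

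**Direction of the leg-site error.** Two cases show that it is not fixed.
- Thigh pain shortens a participant's walking and the arms are unaffected. The arm clause of Mild fits, while Table 5 gives Grade 2 for interference with activity: possibly too low. The other Mild sentence, only slight discomfort, may still steer the participant away from Mild.
- Thigh pain makes a participant skip one run. The diary's Severe wording fits, while daily activity was not prevented, so Table 5 may give Grade 2: possibly too high.

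**Route of touch-only tenderness.** Pain is correctly marked NONE and no other row applies. What remains is the unprompted free text under other symptoms, general adverse-event questions at visits, and a staff examination whose list omits tenderness.

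**Size.**
- One participant's weight in a cohort proportion: 1/3 = 33, 1/5 = 20 and 1/6 = 17 percentage points.
- Participants a revised form could still reach: Sections 4.1 and 4.2 refer to expression already observed in cohorts A to D. From Table 2, E, F and G have 5 + 5 + 5 = 15 participants. Dosing days are 5×2 + 5×2 + 5×4 = 40.
- Touch-only tenderness: the protocol gives no rate. Assuming 10% to 30% of participants, 0.10×15 = 1.5 to 0.30×15 = 4.5 of those 15 would have it. This is the number at risk of being missed, not the number that would be missed.

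**The case against.** The strongest reply is that the diary does not set the grade. Staff grade each entry on a scale based on activity and must document disagreement with the participant (9.8.2). They assess sites 30 minutes after injection and at visits up to Day 10, ask about adverse events at each visit, and are told to choose the most suitable term from Table 5, which includes tenderness. Participants may write in unlisted symptoms. The tenderness criterion for dose-limiting toxicity (10.10) requires overnight hospitalization, which a missing diary row would not hide.

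Most of this stands, and it limits the point to a risk. It does not close the gap. A NONE gives staff nothing to grade, an arm-use tick does not show whether the leg was limited, and free text depends on the participant thinking of it.

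A reader might infer three stronger conclusions that the documents do not support:
- That the endpoint is biased downward. The second leg-site case above goes the other way, so only misclassification can be claimed for intensity. For tenderness, under-recording is possible but not shown.
- That all reactions are graded by arm use. This is true only of Mild and Moderate pain and itching.
- That one unlabelled row for two injection sites distorts the primary result. The row asks for the day's worst symptom or largest measurement, and 11.3.1 counts each event once per participant on a worst-case basis, so the planned frequency and severity summaries are unaffected. Site-level detail is lost, but no reaction analysis per antibody is specified.

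**Conclusion.** The point holds as a misalignment between the data-collection form and the protocol. Leg-site pain and itching may be misclassified in either direction between visits, and Grade 1 tenderness may be under-recorded, in a primary safety endpoint. It should be corrected, but it does not show that the safety results are wrong.

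The number of affected entries cannot be estimated: the share of leg injections and the rate of touch-only tenderness are not given, and the yield of staff questioning and free text is unknown. The practical reach of a correction is at most 15 participants and 40 dosing days, on the inference that cohorts A to D have been dosed.

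**What to change.** In Appendix A, on every diary day:
1. Replace the reference to the arm in the Mild and Moderate anchors with the injected arm or leg, or reuse the activity-based wording the diary already has for other symptoms.
2. Add a tenderness row using Table 5 wording.

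In 9.4.1 and 9.8.2, add tenderness to the local-reaction lists. A site label per entry is optional; it would add detail but does not affect the planned summary.

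The cost is a slightly longer form and matching CRF fields, with no new visit or test. The real drawback is comparability: later cohorts would be asked about tenderness and earlier ones were not, and the pain anchors would differ. Tenderness and pain intensity should therefore be reported with a note of the diary version used, and a higher tenderness rate in later cohorts should not be read as a dose or regimen effect without that caveat.
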